A disposable UST device (Jada, Organon), was approved by the US Federal Drug Agency, based on an observational study in North America. The Jada device has become standard of care in many US institutions, with reassuring post-marketing data on 800 cases.⁴ Large observational studies report that suction tamponade (Jada) compared with balloon tamponade (Bakri) reduce severe morbidity.^{5,6}

Small, randomized trials have found better outcomes with simple suction tube tamponade than balloon tamponade, and significantly less experience of severe pain.^{7,8}

Suction tamponade to arrest uterine bleeding is equally relevant to vaginal and caesarean birth (CB). Post-marketing data on 800 cases treated with the Jada device included an 84% success rate among 270 cases following CB.⁴ However, use of the Jada device following CB would be restricted to cases in which the uterine cervix is sufficiently dilated to accommodate the bulky device.

Caesarean birth (CB) is increasing globally, with concomitant increase in caesarean morbidity and mortality. CB complications have been identified by WHO as a major global health problem. Blood loss at CB has been measured as mean 558mL (± 496 mL), with 5% losing >1300 mL.⁹

There are three distinct potential benefits of uterine suction tube placement at CB. Firstly, during closure of the uterine incision, the suction tube acts as an efficient 'sump' suction to clear blood from the surgical field, facilitating closure. Secondly, after closure of the uterine incision, the suction tube minimises blood loss by rapidly stimulating and maintaining uterine contraction and retraction. Thirdly, the presence of the STUT catheter efficiently monitors blood loss both during and after surgery, allowing prompt treatment of any PPH.

We have identified and reported on a low-cost (GBP 0.50p), widely available soft plastic catheter (the Levin FG 24 stomach tube) for STUT.^{10,11}

WHO is conducting a large, randomised trial of treatments for refractory PPH in Vietnam (RED). Our preliminary data on the improvised STUT method was evaluated by the WHO ethics and scientific committees and approved for use as the only suction tamponade method in this trial (versus the Sinapi Ellavi balloon

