Control: This is a pilot proof of concept study with sample size insufficient for a formal randomized comparison. In order to have a valid comparator, participants will be randomly allocated to an intervention and control group (approx. 40 per group). No p values will be calculated. Comparisons will be as risk ratios or mean differences with 95% confidence intervals.

Outcomes

Baseline demography and clinical data will be recorded.

Primary: The primary outcome is the combined frequency of adverse device effects and device deficiencies up to discharge from hospital.

Adverse device effects (ADEs) encompass any adverse event with a reasonable causal relationship resulting from insufficient or inadequate instructions for use; problems with the deployment, implantation, installation, or operation of the device; malfunction of the device; or user error or intentional misuse of the device. They will include device deficiencies such as device expulsion / falling out of the uterus, failed maintenance of suction pressure and tube blockage.

A Serious Adverse Device Effect (SADE) is an adverse device effect that has resulted in any of the consequences characteristic of a serious adverse event. An example of this would be the need for further intervention to treat trauma caused by the device (e.g. sutures, laparotomy, etc).

Secondary efficacy outcomes will include:

- 1. Measured blood loss within 30 minutes after insertion (ml)
- 2. Blood loss >500ml
- 3. Blood loss >1000ml
- 4. Efficiency of suction (assessed through ultrasound assessment of residual blood in the uterus at 30 minutes or blood expressed from the uterus after tube removal)
- 5. Blood pressure, pulse and shock index 15 minutes after vaginal birth or caesarean
- 6. Change in routinely collected haemoglobin levels pre delivery to post delivery
- 7. Blood transfusion
- 8. ICU admission
- 9. Death
- 10. Functionality and acceptability:
 - a. Active bleeding from the uterus continuing for more than 10 minutes (main efficacy outcome).
 - b. Any adverse event
 - c. Pain experienced (No pain/Mild /Severe/Unbearable)
 - d. Need for Additional interventions to stop bleeding (e.g. more uterotonics, compressive measures, UBT, laparotomy, hysterectomy)
 - e. Was STUT effectively inserted? (Yes/No/Unknown)
 - f. How easy was it for health care providers to insert the Suction Tube Uterine Tamponade (easy/moderately difficult/Difficult/failed)

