- g. Did the suction tube remain in place in the uterus until removal (Yes/No/Unknown)
- h. Did the suction tube establish a good seal (no loss of suction) (Yes/No/Unknown)
- Did the suction tube interfere with or facilitate examination for and management of lower genital tract bleeding after vaginal birth (Facilitated/Interfered/Neither/not applicable/Unknown)
- j. Did the suction tube interfere with or facilitate surgical exposure during caesarean birth (Facilitated/Interfered/Neither/Unknown)
- k. Was there any blockage of the suction tube (Yes/No/Unknown)

Recruitment and consent

We plan to approach women at increased risk of PPH awaiting caesarean or induction of labour, pre-labour or in early labour and provide written and/or video information to them. They will be given time to discuss participation with friends and family and then invited to provide signed consent. Consent will be confirmed verbally immediately after birth, prior to device insertion.

Sample size

We aim to use the U-STAT in 40 participants, with a minimum of 25% being vaginal births and 25% caesarean section. 35 participants will provide 90% confidence that the true rate of adverse device effects and device deficiencies is under 10% (+/-10%). The sample is increased to 40 to account for any unexpected procedural difficulties in the first 5 recruits.

Procedures

Participating sites will be supplied with a 'PPH emergency trolley' containing all the supplies needed for STUT and emergency treatment of PPH, as well as forms for screening, enrolment, randomization and data collection. After vaginal birth, the suction tube will be inserted under sterile conditions transvaginally into the uterine cavity. Suction will be applied either with the manual suction device or with a surgical suction unit, set at 100mmHg suction pressure. If there is excessive bleeding which is not controlled by the STUT, the suction tube will be removed and management continued according to local protocols. If effective, the STUT suction will be interrupted every 30 minutes, and removed as soon as bleeding is controlled without suction. All other care will follow local practice. Blood loss will be measured from enrolment until bleeding is controlled (minimum 30 minutes), using a blood collection drape or Maternawell tray, plus blood collected in the UVT suction bottle, surgical suction and swabs.

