Enrolment will take place immediately after birth of the baby when the participant's name is entered in the enrolment register and allocation takes place by opening the next in a consecutively numbered series of opaque sealed envelopes with allocation cards in computer-generated random sequence in balanced blocks of variable size, stratified by mode of birth. Participants will remain in the trial whether or not the intervention is applied, on the 'intention to treat' principle. Good Clinical Practice (GCP) procedures will be followed.

A clinical checklist will be completed by the attending clinician, which will form part of the patient clinical record. Data will be entered onto paper or electronic CRFs by the research staff.

Quality control will be performed on-site: the research staff will be responsible for ensuring that the CRFs are correctly filled out. Completed CRFs will be checked against the original patient records for correct completion. Any discrepancies will be immediately addressed.

Data management

Because of the small number of participants and limited data per participant, complex data entry strategies will not be needed. Data will be entered onto paper or electronic CRF's, checked for accuracy at source, and stored in a locked filing cabinet or password-protected computer. The data will be entered onto an excel spreadsheet and analysed using Epi Info software.

Adverse events and serious adverse events, whether thought to be related to the trial intervention or not, will be recorded by the site PIs on standard adverse events forms which will be submitted to the University ethics committee and DSMC.

Data protection procedures

The following measures will be taken to ensure participant confidentiality:

- Trial data sets for each participant will be identified by a unique ID number, not the participant's name
- The trial register of names and trial ID numbers, and consent forms will be kept separate from the CRFs
- Trial documents will be kept securely under lock and key and will not be accessible, other than to the research teams
- Data will be entered by trial ID number onto a password-protected database to which only trial staff will have access
- The trial report will not contain the names of any participants
- After completion of the trial, the trial documents will be kept under lock and key for five years

Personal information

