19. Tamponade device inserted? 2=Other tube*; 3=Ellavi; 4 = Other	· ·				
20. Time device inserted:		:			

21. Ease of insertion? 1=easy, 2=mod.diff, 3=difficult		
22. Device stable in uterus? 0=No; 1=Yes		
23. Tube air leak? 0=No; 1=Yes; 3=No tube		
25. Effect of device on exam/mx? 1. Facilitated, 2. Interfered, 3.Neither		
26. Exam obscured by blood from ut: 0=No; 1=Yes		
27. Time bleeding stopped.	:	
28. Time vital signs check (+ 15min)	:	
29. Syst BP mmHg		
30. Diast BP mmHg		
31. Pulse /m		
32. Additional oxytocin 0 = No 1= Yes		
33. Additional erg-/syntomentrine 0 = No 1= Yes		
34. Additional misoprostol 0 = No 1= Yes		
35. Additional tranexamic acid 0 = No 1= Yes		
36. Time blood collection measured (>30 min)	:	
37. Blood volume excluding suction jar (ml)		
38. Blood volume in suction jar (ml)		
39. Blood expelled ex ut. after removal of device or after 30 min in control group (ml)		
40. If bleeding persists, measured blood loss post 30min		
41. Laparotomy 0 = No 1= Yes		
42. Compression sutures 0 = No 1= Yes		
43. Uterine devascularization 0 = No 1= Yes		
44. Hysterectomy 0 = No 1= Yes		
45. Other procedure 0 = No 1= Yes*		
46.ICU admission 0 = No 1= Yes		
47. Organ failure 0 = No 1= Yes*		

48. Death 0 = No 1= Yes		
49. Blood transfusion (number of units RBCs)		
50. First Haemoglobin after bleeding controlled (g/dL)		
51. Highest temperature (deg C)		
52. Endometritis 0 = No 1= Yes 9=Unknown		
53. Other complications 0 = No 1= Yes* 9=Unknown		
53. Date of Discharge (DD/MMM/YY)	/ /	

Completed by (initials) :	Date completed	(dd/mmm/yy)
Completed by (initials) .	Date completed	(dd/IIIIIII/yy

Vaginal birth Clinical checklist (remains in hospital records)

Equity for Suction Tamponade Access to treat postpartum haemorrhage: The ESTA project

	1.	○ Consent signed
	2.	Confirm with Mother that still happy with consent
	3.	Ostudy trolley is available with register, U-STAT suction tubes, working suction
	4.	Clean drape or Maternawell tray available
	5.	\bigcirc Manual suction device ready with vacuum pumped or suction machine pressure set to 100mmHg – block tubing to check
	6.	After baby born position drape/Maternawell tray below the buttocks
Aft	er p	lacenta delivered completely:
	7.	Examine vaginally to exclude major lower genital tract trauma
	8.	O Note the time, 24 hr: H H : M M
	9.	○ Open next numbered envelope and note allocation: ○ STUT* ○ Control
	10.	*Insert U-STAT tube to fundus of uterus and start suction

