	11.	\bigcirc *Insertion of tube; \bigcirc easy, \bigcirc moderately difficult, \bigcirc difficult, \bigcirc Failed, \bigcirc not done
	12.	Alternative Management
	13.	*Time tube insertion procedure completed 24 hr: H H : M M
	14.	*Check tube/balloon stable in uterus Yes / No / Onot used
	15.	Ocontinue routine care including repair of bleeding tears
	16.	*Effect of device on exam/mx of lower genital tract bleeding? Facilitated; Interfered; Neither; Unknown
	17.	○ Note the time per vaginal bleeding stopped. 24 hr: H H : M M
	18.	○ 15 minutes after insertion (10 above) note time 24 hr: H H : M M
		Systolic BP Diastolic Pulse
	19.	○ 30 minutes after insertion, note time. 24 hr: H H : M M
	20.	
		ml ml
	21.	Replace empty tray, expel blood from the uterus by fundal massage (into tray)
	22.	○ Measure blood loss in tray = RESIDUAL
		ml ml
	23.	*disconnect suction. If no bleeding in 10 minutes, remove U=STAT tube
	2/	*If bleeding continues replace empty tray continue suction plus other measure

25. When bleeding stopped, measure blood loss in tray = Secondary blood loss
ml ml
26. *Measure blood loss in suction bottle
ml ml
27.
○ None
The participants will be followed till discharge and the outcome data, as well as any complications, recorded.

Caesarean birth Clinical checklist (remains in hospital records)

Equity for Suction Tamponade Access to treat postpartum haemorrhage: The ESTA project

	1.	○ Consent signed
	2.	Oconfirm with Mother that still happy with consent
	3.	OStudy trolley is available with register, U-STAT suction tubes, working suction
	4.	Clean drape or Maternawell tray available for post-op use
	5.	○ Manual suction device ready with vacuum pumped or suction machine pressure set to 100mmHg – block tubing to check
	6.	\bigcirc After birth of baby, open next numbered envelope and note allocation: \bigcirc STUT* \bigcirc Control
Aft	er p	placenta delivered completely:
	7.	○ Note the time, 24 hr: H H : M M
	8.	\bigcirc *Insert U-STAT tube to fundus of uterus and lower end through cervix and vagina, ask assistant to connect and start suction
	9.	\bigcirc *Insertion of tube; \bigcirc easy, \bigcirc moderately difficult, \bigcirc difficult, \bigcirc Failed, \bigcirc not done
	10.	. Alternative Management
	11.	. *Time tube insertion procedure completed 24 hr: H H : M M
	12.	. Continue uterine closure
	13.	*Effect of device on visualisation for uterine closure? \(\text{Facilitated}; \text{Interfered}; \) Neither; \(\text{Unknown}\)

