	14.	. Time uterus closed 24 hr: H H : M M
	15.	. Measure blood volume in suction bottle = pre-suction volume:
		ml ml
	16.	*Note the time bleeding through suction tube stopped. 24 hr: H H : M M
	17.	. O 15 minutes after placental delivery (7 above) note time 24 hr: H H : M M
		Systolic BP Diastolic Pulse
	18.	. After skin closure, estimate surgical blood loss (excluding U=STAT tube drainage)
		ml ml
	19.	. O In recovery room: Place drape or Maternawell tray under participant's buttocks
	20.	
	21.	. O 30 minutes after placental delivery (7 above), note time. 24 hr: H H : M M
	22.	. Swab vagina and measure blood loss in drape/tray = postop blood blood

23. O Place new tray or drape under participant and express blood from uterus -
Measure blood loss in drape/tray = RESIDUAL blood
ml ml
24. *Disconnect suction, if no bleeding after 10 minutes, remove U-STAT tube. If
bleeding resumes, reconnect suction and manage as per hospital protocol
25. *Measure blood loss in suction bottle
ml ml
26. *Suction tube problems: Fell out; blocked; leaking; Poor suction
○ None

ml

The participants will be followed till discharge and the outcome data, as well as any complications, recorded.

Participant questionnaire (Vaginal birth Intervention group only)

Protocol Title: Equity for Suction Tamponade Access to treat postpartum haemorrhage: The ESTA project			
Site Number:	Subject ID:	Date:(dd/mmm/yy)	
Dear Participant, thank you for assisting us with the ESTA project. Pease would you answer the following questions. There are no right or wrong answers. Please just give us your personal opinions. Please feel free not to answer if you prefer not to.			
Questionnaire		Comment/Notes	
*After the hirth of your ba	by a tubo was	T	
*After the birth of your baby, a tube was inserted to your uterus to help reduce bleeding Please could you describe the pain you experienced? 0=No pain; 1 = Mild pain; 2 = Severe pain; 3 = Unbearable pain; 4 = unsure; 9 = no data			
*Please could you describe when the tube was removed = Mild pain; 2 = Severe pain Unbearable pain; 4 = unsure	d? 0=No pain; 1 u; 3 =		
*Please could you describe overall about the suction tub 0= fine; 1 = uncomfortable b = Unacceptable; 3 = Unbear unsure; 9 = no data	pe procedure? out acceptable; 2		
Thank you for assisting with this questionnaire			

Date completed

(dd/mmm/yy)

Completed by (initials):

Participant questionnaire (Caesarean birth Intervention group only)

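### Blood collection starts before the device is in place and is never split, so the recorded volume is not the post-insertion loss that secondary outcome 1 defines

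*Protocol*

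**What the plan says.** The Protocol gives more than one starting point for blood loss.

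- **Outcomes, secondary 1:** "Measured blood loss within 30 minutes after insertion (ml". Secondary 2, "Blood loss >500ml", and secondary 3 (the 1000 ml threshold) state no starting point.
- **Procedures:** "Blood loss will be measured from enrolment until bleeding is controlled (minimum 30 minutes". The section During recruitment dates that moment: "Enrolment will take place immediately after birth of the baby".
- **Vaginal birth Clinical checklist:** item 6 reads "After baby born position drape/Maternawell tray below the buttocks". The placenta, the vaginal examination (item 7), a time entry (item 8), the envelope (item 9) and insertion with suction (item 10) follow. The first tray change is item 21, after the 30-minute point at item 19: "Replace empty tray, expel blood from the uterus by fundal massage (into tray".
- **Caesarean birth Clinical checklist:** the envelope is opened after the baby is born (item 6), a time is noted after the placenta (item 7), and the tube is inserted and suction started (item 8). A bottle reading labelled as pre-suction is taken at item 15, after uterine closure. Item 18 reads: "After skin closure, estimate surgical blood loss (excluding U=STAT tube drainage".
- **CRF:** item 37 is one volume for everything outside the suction jar. Items 38 to 40 cover the jar, blood expelled at the end, and loss after 30 minutes. No field holds loss from before the device.

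**The concern.** Blood lost before the tube is in place cannot respond to it. If that blood shares a container and a CRF field with later loss, the figure reported for outcome 1 is a different quantity from the one named. It carries extra between-woman variation into the comparison.

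The trial is meant to indicate effectiveness and suitability for a larger randomised trial, and its comparisons are to be mean differences and risk ratios with 95% confidence intervals. An avoidably wide interval, or a risk ratio read as the device's effect on later bleeding when it describes total bleeding, would be a poor basis for planning that trial. An analysis plan cannot repair this, because the volume needed for the split would never have been recorded.

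**Working it through.** The Protocol states no precision for blood loss, so there is no figure of its own to reproduce. The point rests on the order of steps; the arithmetic only gives its size.

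**Step 1. Vaginal birth.** Three quantities enter the same tray: A, birth to envelope; B, envelope to insertion; C, the 30 minutes after insertion. Outcome 1 is C. The tray holds A + B + C, because nothing between items 6 and 10 reads or empties it. Item 20 is not legible in the copy at hand and is presumably the 30-minute reading. Items 6 to 10 are legible, so this does not alter the result. Controls have no insertion, yet vaginal items 18 and 19 count their times from it.

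**Step 2. Caesarean birth.** Item 18 is one estimate with no start point, excluding only tube drainage. Read naturally, it includes loss from incision to birth. Item 15 could have separated earlier bottle volume, but suction starts at item 8, so by uterine closure the reading may already include blood cleared while the device was working. It also has no evident CRF field.

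**Step 3. Time origins compared.**

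| Source | Start of measurement |
|---|---|
| Outcomes, secondary 1 | insertion |
| Procedures with During recruitment | enrolment, immediately after birth |
| Vaginal checklist | birth for the tray; insertion for the 15- and 30-minute clocks |
| Caesarean checklist | unstated for item 18; placental delivery for the 15- and 30-minute clocks |

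**Step 4. Precision of the mean difference.** Inputs: SD 496 ml from Background ("Blood loss at CB has been measured as mean 558mL (± 496 mL), with 5% losing >1300 mL") and 40 per arm from Methods. The share of variance arising before the device is not in the Protocol; 25% and 50% are assumed, with earlier and later loss independent.

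- All loss: 1.96 × 496 × √(2/40) = 217 ml.
- Later loss only, 25% earlier: 217.4 × √0.75 = 188 ml (13% narrower).
- Later loss only, 50% earlier: 217.4 × √0.50 = 154 ml (29% narrower).

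**Step 5. Is the mean difference biased?** Suppose (assumed) that the device cuts later loss by 30% and that earlier loss is a share f of the mean of 558 ml. The true difference is 0.30 × 558 × (1 − f): 125.6 ml at f = 25% and 83.7 ml at f = 50%. Earlier loss has the same expectation in both arms and cancels, so counting it leaves the difference unchanged.

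**Step 6. Threshold outcomes.** A simulation used gamma-distributed loss with mean 558 ml and SD 496 ml, independent earlier and later parts, the same 30% reduction, and 2 million women per arm. It gave these risk ratios:

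| Earlier share (assumed) | >500 ml, later loss only | >500 ml, all loss | >1000 ml, later loss only | >1000 ml, all loss |
|---|---|---|---|---|
| 25% | 0.608 | 0.746 | 0.373 | 0.553 |
| 50% | 0.563 | 0.835 | 0.340 | 0.694 |

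The all-loss ratios lie closer to 1. They are correct ratios for total loss and would mislead only if read as ratios for loss after the device.

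**The case against.** The strongest reply is that the checklist follows the Protocol's own rule. Procedures measures from enrolment, enrolment is placed immediately after birth, and item 6 puts the tray down at that moment. On this view the container is fresh at the right time, and only the wording of outcome 1 is out of step. For vaginal birth this largely stands: redefining outcome 1 as loss from birth would make the documents agree. It would also give up the quantity now named. It would not settle caesarean item 18, and the vaginal checklist would still open the allocation envelope after the placenta and examination rather than immediately after birth.

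A reader might go further than the documents allow in three ways:

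- **That the comparison is biased.** It is not: earlier loss is balanced in expectation by randomisation, so the mean difference loses only precision.
- **That the risk ratios for 500 and 1000 ml are distorted.** Those outcomes state no starting point, and cumulative loss from birth is a legitimate target, for which the ratio nearer to 1 is the right answer.
- **That item 18 is written to span the whole operation.** It does not say so. Procedures could be read as limiting the surgical count to loss after enrolment, and item 15 shows that some separation was intended.

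It is also fair to say that the size is illustrative. The SD comes from caesarean births but the sample mixes both modes, the variance shares have no source in the Protocol, and the scaling needs independence. The outcomes are secondary, in an exploratory trial without p values.

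**Conclusion.** The point holds as a mismatch between definition and measurement. As the checklists stand, outcome 1 cannot be obtained for vaginal births and is not clearly obtainable for caesarean births, and the Protocol gives conflicting time origins.

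The statistical cost is a wider interval for an unbiased mean difference: a half-width of 217 ml against about 188 to 154 ml. This assumes SD 496 ml in both modes of birth, 25 to 50% of the variance arising earlier, and independent parts. For the 500 and 1000 ml outcomes, the consequence is one of interpretation: the target must be stated as cumulative, or the ratios will be taken for something they are not.

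The primary outcome (device effects and deficiencies) and the main efficacy outcome (10a, bleeding continuing beyond 10 minutes) do not use these volumes. The change is worth making before recruitment because it is cheap and cannot be made afterwards.

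**What to change.** 1. **Vaginal checklist:** between items 8 and 9, before the envelope is opened, read and replace the tray in both arms. The reading is then made without knowledge of the allocation.
2. **Caesarean checklist:** move the existing pre-suction bottle reading from item 15 to before device suction starts, at the same point in both arms, for example at item 7. State the start point of the surgical estimate at item 18.
3. **CRF:** add a field for the earlier volume (pre-allocation at vaginal birth, pre-suction at caesarean), so that item 37 can be separated.
4. **Outcomes and Procedures:** adopt one time origin that exists for controls as well, and report outcome 1 on the later volume. State that outcomes 2 and 3 are cumulative, and report beside them the number already above each threshold at allocation where this was measured.

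The cost is one short extra reading at a busy moment, a relocated reading at caesarean, and a CRF field. Some limits remain. At vaginal birth, the short interval from envelope to insertion stays in the later volume. At caesarean, the reading follows the envelope, so staff know the allocation, and the bottle does not capture blood on swabs. Splitting swabs in mid-operation would be harder and is not asked for.

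### Vaginal birth checklist: the tray change before the Secondary blood loss reading is a device-arm step only, so later blood loss is collected differently in the two arms

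*Protocol*

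**What the plan says.** The Vaginal birth Clinical checklist in the Protocol marks some steps with a star. Item 9 shows what the star means: "Open next numbered envelope and note allocation: ○ STUT* ○ Control". It is printed beside the device allocation and not beside control.

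The steps that matter here run as follows.

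- Item 21, no star: "Replace empty tray, expel blood from the uterus by fundal massage (into tray".
- Item 22, no star: "Measure blood loss in tray = RESIDUAL".
- Item 23, starred: suction is disconnected and the tube is removed if bleeding has stopped.
- Item 24, starred: "If bleeding continues replace empty tray continue suction plus other measure".
- Item 25, no star: "When bleeding stopped, measure blood loss in tray = Secondary blood loss".

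The ESTA Study Clinical Record Form has two separate fields for these volumes. CRF 39 is "Blood expelled ex ut. after removal of device or after 30 min in control group (ml", which names controls explicitly. CRF 40 is "If bleeding persists, measured blood loss post 30min", with no restriction by arm.

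The Procedures section sets the measurement span: "Blood loss will be measured from enrolment until bleeding is controlled (minimum 30 minutes". The Outcomes section lists blood loss above 500 ml and above 1000 ml without a time window, and separately lists measured loss within 30 minutes of insertion.

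**The concern.** A control still bleeding after the RESIDUAL reading goes from item 22 straight to item 25, with no printed instruction to empty or change the tray. A device-arm woman in the same position is given an empty tray first. The same label, Secondary blood loss, can therefore stand for two different quantities depending on allocation.

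The Control paragraph says that women are randomised so that there is a valid comparator, and that results will be given as risk ratios or mean differences with confidence intervals. A collection step that depends on the arm works against that purpose. An analysis plan can define how the fields are summed, but it cannot tell afterwards whether a given control's tray was changed.

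**Working it through.** No sample size, power or stated figure is involved, so there is nothing of the plan's own to reproduce. The check traces the steps by arm and follows the volumes.

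**Meaning of the star.** Item 9 attaches it to STUT. The other starred vaginal items outside the pair in question (10, 11, 13, 14, 16, 23 and 26) are all device steps, which agrees with that reading.

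**Symbols.** A is the tray reading at 30 minutes, R the RESIDUAL volume and S the true loss after the RESIDUAL reading. I take A to be item 20, from its position between the 30-minute time note and the tray change, since its text is not legible in the copy at hand. Suction-bottle volume is left out. Neither simplification changes the excess found below.

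**A woman who keeps bleeding after item 22:**

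| | Item 22 | Tray change before item 25 | Item 25 | Sum of readings |
|---|---|---|---|---|
| Device arm | R | yes (item 24) | S | A + R + S |
| Control, item 25 applies to both arms | R | none printed | R + S | A + 2R + S |
| Control, item 25 continues item 24 | R | none | not taken | A + R |

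The true total is A + R + S in every row. On the literal reading the control's recorded total is too high by (A + 2R + S) − (A + R + S) = R. On the continuation reading it is too low by (A + R + S) − (A + R) = S.

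**Illustration.** The volumes are assumed, because the Protocol gives none for these readings: A = 300 ml and S = 50 ml.

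| R (ml) | True total | Control, literal | Control, continuation |
|---|---|---|---|
| 50 | 400 | 450 | 350 |
| 100 | 450 | 550 | 400 |
| 200 | 550 | 750 | 500 |

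At R = 100 the literal reading moves a control wrongly above 500 ml. At R = 200 the continuation reading wrongly leaves her at 500 ml, so she is not counted as above it.

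**Does measuring imply emptying?** The form treats a fresh tray as its own step elsewhere: vaginal items 21 and 24, and caesarean item 23. Reading a tray is not written as emptying it.

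**How many women.** The target is about 40 controls. The Sample size section sets minimums of 25% vaginal and 25% caesarean for device participants. If the same limits apply to controls, vaginal-birth controls number between 0.25 × 40 = 10 and 0.75 × 40 = 30, and only those still bleeding after item 22 are exposed. One misclassified control out of 40 moves a threshold proportion by 1/40 = 2.5 percentage points.

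**The case against.** The double count depends on several things that the Protocol does not state. Staff would have to leave already measured blood in the tray and read it again, although items 22 and 25 carry different labels. Item 25 would have to be copied unadjusted into CRF 40. CRF 39 and 40 would then have to be added, and no formula is given. All of this stands, and it makes the inflation conditional. Adding is nevertheless the natural use of two separate fields when loss is measured from enrolment until control.

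Item 25 follows directly on a conditional, starred step and may be meant as its continuation. The stars are also not a perfect arm code, because items 18 and 19 are unstarred yet timed from an insertion that controls do not have. The text is imperfectly legible around items 20, 24 and 27, although the stars on items 23, 24 and 26 survive, so the absence of one on item 25 is probably real. This objection also stands, but it changes the direction of the bias and does not remove the difference between arms.

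The section headed Before recruitment promises written guidelines, training and a pilot of the procedures and forms, which might catch the problem. That is a reason to correct the form at that stage.

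A reader might infer that the form makes the device look effective when it has no effect, or try to attach a spurious risk ratio to it. The documents do not support either. A ratio would need the distribution of blood loss at vaginal birth, the size of RESIDUAL and the share of controls still bleeding, and none of these is given. The one distribution quoted in the Background (mean 558 ml, SD 496 ml) is for caesarean birth, where this checklist is not used.

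**Conclusion.** The point holds as a defect of the form. As printed, loss after the RESIDUAL reading is collected differently by arm at vaginal birth. On the literal reading a control's summed total is too high by exactly R, which favours the device. On the alternative reading it is too low by S, which favours control. The first result assumes that the tray is not emptied at item 22 and that CRF 39 and 40 are added.

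The reach is limited to vaginal-birth controls who keep bleeding, and to the >500 ml and >1000 ml outcomes if these include loss after 30 minutes. The primary outcome (device effects and deficiencies), the main efficacy outcome (active bleeding beyond 10 minutes) and 30-minute blood loss are not affected. No p values are planned and the study is described as too small for a formal comparison, so this is a possible bias in secondary estimates and not a demonstrated one. It is still worth correcting, because it cannot be repaired once the data are collected.

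**What to change.** On the Vaginal birth Clinical checklist:

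- Split item 24. Make replacing the tray with an empty one, straight after the RESIDUAL reading, an unstarred step for both arms. Leave the suction instruction starred and unchanged.
- Mark item 25 explicitly as applying to both arms.

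Beside the Clinical Record Form, or in the analysis plan, state that total blood loss is the sum of CRF 37 to 40 with no volume counted twice, and say whether the >500 ml and >1000 ml outcomes use that total or the 30-minute loss.

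The cost is one or two lines on the form. It needs no extra participants or procedures and does not alter clinical management.
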